5.4.9. Dose Reductions

Dose reductions of PF-05082566 and/or mogamulizumab may be required based on the worst toxicity experienced in the previous administration or previous cycle (see [Table 7](#)).

No specific dose adjustments are recommended for Grade 1/2 treatment-related toxicity. However, investigators should always manage their patients according to their medical judgment based on the particular clinical circumstances.

Patients experiencing recurrent and intolerable Grade 2 non-hematologic toxicity may resume dosing, with specific dose modifications detailed in Section 5.4.9.1, once recovery to Grade ≤ 1 or baseline is achieved.

Once a patient has a dose reduction in PF-05082566 and/or mogamulizumab for a drug-related toxicity, the dose will not be re-escalated. Patients requiring more than one dose reduction will be withdrawn from treatment unless otherwise agreed between the investigator and the Sponsor.

5.4.9.1. Dose Modification Guidelines

Table 7 below shows the PF-05082566 and mogamulizumab doses available for dose reduction in this study. Suggested dose modification guidelines are presented in [Table 8](#) below. Both study drugs or mogamulizumab only should be held for the listed toxicities with dose modifications as suggested.

Table 7. Available Doses for Dose Reduction

PF-05082566* (mg/kg)	Mogamulizumab (mg/kg)
2.4	0.5
1.2	
50 mg flat dose**	
0.6	

*Intermediate doses could be used for dose-reduction based of DLTs observed.

** To be used for the 100 mg flat dose cohort.

Patients experiencing a DLT may resume dosing at the next lower dose level (if applicable) once adequate recovery is achieved.

Recommended dose reductions are illustrated in [Table 8](#). **The guidelines apply to both drugs when co-administered or to mogamulizumab alone (when applicable).** These recommendations are applicable for all cycles.

Table 8. Dose Modification Guidelines for Treatment Related Adverse Events

Toxicity	Grade	Hold Treatment*	Criteria for Treatment Restart*	Dose Modification*	Discontinue Patient* (after consultation with Sponsor)
Hematologic Toxicity meeting any of the criteria in Section 3.2 .	3	Yes	Hold treatment until toxicity resolved to Grade ≤ 1 (Grade 2 for ANC)	Decrease dose by one dose level (based on Table 7).	If toxicity does not resolve to Grade ≤ 1 or does not allow retreatment within 4 weeks of last infusion, consider permanent discontinuation after consultation with the Sponsor.
	4	Yes	Hold treatment until toxicity resolved to Grade ≤ 1 (Grade 2 for ANC)	Decrease dose by one dose level (based on Table 7).	If toxicity does not resolve to Grade ≤ 1 or does not allow retreatment within 4 weeks of last infusion, consider permanent discontinuation after consultation with the Sponsor.
Non-Hematologic Toxicity	1 and 2 (if Grade 2 is not recurrent/intolerable)	No	N/A	Continue at same dose level.	N/A
	2 (only if recurrent/intolerable)	Consider holding	Hold treatment until toxicity resolved to baseline or Grade ≤ 1	Continue at same dose level.	If toxicity does not resolve to baseline or Grade ≤ 1 within 4 weeks of last infusion, consider permanent discontinuation after consultation with the Sponsor.
	3 (if persisting when maximally treated)	Yes	Hold treatment until toxicity resolved to baseline or Grade ≤ 1 (or, at the investigator discretion, to Grade ≤ 2 if not considered a safety risk for the patient). For laboratory AEs other than LFTs only: resolved to Grade ≤ 2 and asymptomatic. For LFTs: resolved to baseline or Grade ≤ 1 .	Decrease dose by one dose level.	If toxicity does not resolve to baseline or Grade ≤ 1 (or, at the investigator discretion, to Grade ≤ 2 if not considered a safety risk for the patient) within 4 weeks of last infusion, consider permanent discontinuation after consultation with the Sponsor (except as noted in Section 5.4.9.1 for laboratory AEs). Permanent discontinuation should be considered for any life-threatening event.

Table 8. Dose Modification Guidelines for Treatment Related Adverse Events

Toxicity	Grade	Hold Treatment*	Criteria for Treatment Restart*	Dose Modification*	Discontinue Patient* (after consultation with Sponsor)
	4	Yes	Hold treatment until toxicity resolves to baseline or Grade ≤ 1 . For laboratory AEs other than LFTs only: resolved to Grade ≤ 2 and asymptomatic. For LFTs: resolved to baseline or Grade ≤ 1 .	Decrease dose by one dose level	If toxicity does not resolve to baseline or Grade ≤ 1 within 4 weeks of last infusion, consider permanent discontinuation after consultation with the Sponsor. Permanent discontinuation should be considered for any life-threatening event.

*Both drugs (Day 1 of each cycle) or mogamulizumab only (when applicable);

PF-05082566 and mogamulizumab (if applicable) doses will be modified based on dose levels listed in [Table 7](#).

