5.4.6. Recommended Dose Modifications

Every effort should be made to administer study treatment (ie, PF-05082566 and mogamulizumab) at the planned dose and schedule.

In the event of significant toxicity dosing may be delayed and/or reduced as described below. In the event of multiple toxicities, dose modification should be based on the worst toxicity observed. Patients are to be instructed to notify investigators at the first occurrence of any adverse symptom.

Patients who experience an AE meeting the definition of a DLT may be removed from treatment, based on the dose modification guidelines listed in [Section 5.4.9](#) and in consultation with the Sponsor.

Dose modifications may occur in three ways:

- Within a cycle: dosing interruption until adequate recovery and dose reduction, if required, during a given treatment cycle;
- Between cycles: next cycle administration may be delayed due to persisting toxicity when a new cycle is due to start;
- In the next cycle: dose reduction may be required in a subsequent cycle based on toxicity experienced in the previous cycle.

Investigators are encouraged to employ best supportive care according to local institutional clinical practices and according to the guidance for selected adverse events provided below.

Dose modifications will be reported in the CRF.

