5.4.7. Dose Interruptions

Patients experiencing Grade 3 or 4 potentially treatment related toxicity or intolerable Grade 2 toxicity despite supportive care, should have their treatment interrupted.

Appropriate follow up assessments should be done until adequate recovery occurs as assessed by the investigator. Criteria required before treatment can resume are described in [Section 5.4.8](#), Dose Delays.

Doses may be held as needed until toxicity resolution. Depending on when the adverse event resolved, a treatment interruption may lead to the patient missing all subsequent planned doses within that same cycle or even to delay the initiation of the subsequent cycle.

If the adverse event that led to the treatment interruption recovers within the same cycle, then re-dosing in that cycle is allowed. Doses omitted for toxicity are not replaced within the same cycle. The need for a dose reduction at the time of treatment resumption should be based on the criteria defined in [Section 5.4.9](#), Dose Reductions, unless expressly agreed otherwise following discussion between the investigator and the Sponsor.

In the event of a treatment interruption for reasons other than treatment-related toxicity (eg, elective surgery) lasting >2 weeks, treatment resumption will be decided in consultation with the Sponsor.

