5.4.8. Dose Delays

Re-treatment at the start of any new cycle, intra cycle (when mogamulizumab only is administered), or following treatment interruption due to treatment related toxicity may not occur until all of the following parameters have been met:

- ANC $\geq 1,000/\mu\text{L}$;
- Platelet count $\geq 75,000/\mu\text{L}$;
- Non-hematologic toxicities have returned to baseline or Grade ≤ 1 severity (or, at the investigator discretion, Grade ≤ 2 if not considered a safety risk for the patient).

After all toxicities have recovered within the limits described above, treatment with PF-05082566 and/or mogamulizumab can be resumed.

If a treatment delay results from worsening of hematologic or biochemical parameters, the frequency of relevant blood tests should be increased as clinically indicated.

Intra cycle mogamulizumab dose delay due to treatment related toxicity is not allowed. If, within a cycle, retreatment with mogamulizumab is not possible due to persistent toxicity, the dose/s should be considered as omitted.

Withhold scheduled dose for liver function test (LFT) related AEs (including asymptomatic) Grade ≥ 3 until return to baseline or Grade ≤ 1 severity. In cases of potential liver injury, see [Section 8.6.2](#). In such cases, consultation with a hepatologist should be considered in the decision to initiate treatment with anti-inflammatory medications.

If hematological toxicities do not recover to the above values and non-hematologic toxicity does not resolve to baseline or Grade ≤ 1 (Grade ≤ 2 if not considered a safety risk for the patient) within 4 weeks of last infusion, consider permanent discontinuation after consultation with the Sponsor. With investigator and Sponsor agreement, patients with a laboratory adverse event still at Grade 2 after 4 weeks may continue treatment in the trial only if asymptomatic and controlled.

Permanent discontinuation of study treatment should be considered for any life-threatening event.

If a treatment interruption continues beyond Day 28 of the current cycle, then the day when treatment is restarted will be counted as Day 1 of the next cycle.

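### After Grade 4 non-hematologic toxicity, Section 5.4.8 permits restart at residual Grade 2 where Table 8 requires baseline or Grade ≤1, and the protocol does not say which rule governs

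*Protocol*

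**What the plan says.** Protocol Section 5.4.7 interrupts treatment for Grade 3, Grade 4 and intolerable Grade 2 related toxicity. It then splits the next steps between two sections: "Criteria required before treatment can resume are described in" Section 5.4.8, and "The need for a dose reduction at the time of treatment resumption should be based on the criteria defined in" Section 5.4.9.

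Section 5.4.8 sets one non-hematologic restart condition: "Non-hematologic toxicities have returned to baseline or Grade" 1 or lower, or Grade 2 or lower at the investigator's discretion if this is not judged a safety risk. The original grade plays no part. The section adds that treatment can resume once its limits are met. Its four-week trigger for considering discontinuation ("If hematological toxicities do not recover to the above values and non-hematologic toxicity does not resolve to baseline or Grade" 1 or lower) carries the same Grade 2 allowance.

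Table 8 in Section 5.4.9.1 has its own restart column, arranged by grade. The Grade 4 row reads "Hold treatment until toxicity resolves to baseline or Grade" 1 or lower. The row labelled "2 (only if recurrent/intolerable") also requires baseline or Grade ≤1, although its hold column only advises considering a hold. The investigator's Grade 2 discretion appears in the Grade 3 row alone. The body of Section 5.4.9 repeats the stricter threshold: "Patients experiencing recurrent and intolerable Grade 2 non-hematologic toxicity may resume dosing, with specific dose modifications detailed in Section 5.4.9.1, once recovery to Grade" 1 or baseline is reached.

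The protocol introduces Table 8 as suggested guidance. The SAP defines how dose reductions and delays are tabulated but says nothing on restart thresholds.

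**The concern.** Two sections set the recovery needed before re-dosing, and they differ for the same patient. The more permissive one is the section named for restart criteria. Giving the discretion after Grade 3 and withholding it after Grade 4 looks deliberate in Table 8, and Section 5.4.8 undoes it.

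What is at stake is patient safety and consistency between sites. Section 8.8 describes Grade 4 as life-threatening. Under Section 5.4.8 an intra-cycle mogamulizumab dose cannot be delayed for toxicity; it is given or omitted. At such a visit the two rules can give opposite answers, and two sites could treat identical patients differently while each follows the protocol.

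**Working it through.** The plan states no figure here, so the check sets the rules side by side. It covers non-hematologic, non-laboratory toxicity, excluding infusion reactions (Table 9) and QTcF prolongation (Section 7.1.5), which have their own rules.

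| Worst grade | Section 5.4.7 | Section 5.4.8 restart | Table 8 hold | Table 8 restart | Restart rules agree? |
|---|---|---|---|---|---|
| 2, recurrent or intolerable | interrupt if intolerable despite supportive care | baseline or ≤1; ≤2 at discretion | consider | baseline or ≤1 | No, once held |
| 3 | interrupt | baseline or ≤1; ≤2 at discretion | yes | baseline or ≤1; ≤2 at discretion | Yes |
| 4 | interrupt | baseline or ≤1; ≤2 at discretion | yes | baseline or ≤1 | No |

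1. Of the three non-hematologic rows with a hold or possible hold, one carries the discretion, so 3 − 1 = 2 differ from Section 5.4.8. The four-week discontinuation cells of those two rows differ from the Section 5.4.8 sentence in the same way.

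2. Size after Grade 4, with a baseline of Grade 0 or 1: Table 8 needs recovery of at least 4 − 1 = 3 grades; Section 5.4.8 needs at least 4 − 2 = 2.

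3. Recurrent or intolerable Grade 2: the thresholds conflict only after a hold, because Table 8 leaves the hold optional. That option itself conflicts with Section 5.4.7, which says treatment should be interrupted. The populations are also worded differently: intolerable (5.4.7), recurrent and intolerable (5.4.9), and the two joined by a slash (Table 8).

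4. Laboratory events drop out. For liver tests at Grade 3 or higher, both places require baseline or Grade ≤1. For other laboratory events at Grade 3 or 4, both can accept Grade ≤2, on different conditions (no safety risk; asymptomatic).

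5. Precedence: Section 5.4.7 points to Section 5.4.8 for restart and to Section 5.4.9 for dose. Section 5.4.6 sends DLT patients the other way, to the guidelines in 5.4.9 ("Patients who experience an AE meeting the definition of a DLT may be removed from treatment, based on the dose modification guidelines listed in" that section). Neither cross-reference ranks the two thresholds.

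**The case against.** The best counter-argument is that Section 5.4.8 is a floor and Table 8 a stricter, grade-specific layer above it. A site following Table 8 always satisfies Section 5.4.8, so nobody receives incompatible orders. That last part is true, but the reading does not settle the matter. Section 5.4.8 treats its limits as sufficient for resumption and Table 8 is only suggested, so a site may stop at the floor and still be compliant.

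The safeguards are real. Residual Grade 2 must not be judged a safety risk. Both places say to consider permanent discontinuation for a life-threatening event. Table 8 lowers the dose one level after Grade 4. DLT patients are handled in consultation with the Sponsor, and Section 8.14.1 requires immediate notification of life-threatening SAEs. These narrow the harm; they do not fix the threshold.

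A reader might infer more than the documents support:

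- That Section 5.4.8 alone allows dosing to go on after intolerable Grade 2 with no improvement. Table 8 allows this too when the investigator does not hold.
- That the primary endpoint is distorted. A Grade 4 event already counted as a DLT has full weight (Section 3.1.9) whatever the restart choice. Any effect of re-dosing after Grade 2 on later DLTs is speculation.
- That the Grade 3 row's reference to Section 5.4.9.1 for laboratory events is wrong. Table 8 lies in that section and contains a laboratory rule to which the reference can point.

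**Conclusion.** The inconsistency stands in two of three rows and matters mainly in one. After Grade 4 non-laboratory toxicity, the protocol can be read to allow re-exposure at residual Grade 2, one grade short of what Table 8 requires when baseline is Grade 0 or 1. The Grade 2 row is a lesser conflict, conditional on a hold and mixed with the separate disagreement over whether to hold. This is a safety and consistency point that should be corrected; it does not call the MTD estimation into question. The conclusion rests on the text alone and assumes no precedence rule elsewhere in study materials outside these documents. How many patients would be affected cannot be computed.

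**What to change.** Amend the Section 5.4.8 restart bullet and its four-week sentence as follows:

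- Limit the Grade ≤2 discretion to non-laboratory toxicity whose worst grade was 3.
- Require baseline or Grade ≤1 after Grade 4, and after recurrent or intolerable Grade 2 that led to a hold.
- Keep Table 8's laboratory and liver-test rules, and refer infusion reactions to Table 9 and QTcF prolongation to Section 7.1.5.

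In Table 8, change the Grade 2 hold cell to match Section 5.4.7: hold for intolerable Grade 2 despite supportive care. Use one description of that population throughout.

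Optional tidying in Table 8: the hematologic discontinuation cells omit the Grade 2 allowance for ANC found in their restart cells, and the Grade 4 non-hematologic discontinuation cell omits the laboratory exception in Section 5.4.8. These affect only a review with the Sponsor, not the restart threshold.

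The core change is wording in two places in Section 5.4.8 and one Table 8 cell, plus harmonized terms for the Grade 2 population, with no added visits, procedures or patients. The real cost is that some patients would wait longer to restart, or miss a mogamulizumab dose that the present discretion would allow.

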5.5. Drug Storage

PF-05082566 will be stored at a temperature between 2°C and 8°C (36°F to 46°F).

Mogamulizumab will be stored at a temperature between 2 and 8°C (36 to 46°F), protected from light. The vials should not be vigorously shaken.

The investigator, or an approved representative (eg, pharmacist), will ensure that both PF-05082566 and mogamulizumab are stored in a secured area with controlled access under recommended storage conditions and in accordance with applicable regulatory requirements.

Investigational product should be stored in its original container and in accordance with the drug label. See the DAI for storage conditions and stability of the diluted products.

Storage conditions stated in the SRSDs (ie, IBs of PF-05082566 and mogamulizumab), will be superseded by the storage conditions stated in the labeling.

Site systems must be capable of measuring and documenting (eg, via a log), at a minimum, daily minimum and maximum temperatures for all site storage locations (as applicable, including frozen, refrigerated and/or room temperature products). This should be captured from the time of investigational product receipt throughout study. Even for continuous monitoring systems, a log or site procedure which ensures active daily evaluation for excursions should be documented. The operation of the temperature monitoring device and storage unit (eg, refrigerator), as applicable, should be regularly inspected to ensure it is maintained in working order.

Any excursions from the product label storage conditions should be reported upon discovery. The site should actively pursue options for returning the product to labeled storage conditions, as soon as possible. Deviations from the storage requirements, including any actions taken, must be documented and reported to the Sponsor.

Once an excursion is identified, the investigational product must be quarantined and not used until the Sponsor provides documentation of permission to use the investigational product. Specific details regarding information the site should report for each excursion will be provided to the site.

5.6. Drug Accountability

The investigator's site must maintain adequate records documenting the receipt, use, loss, or other disposition of the drug supplies.

Pfizer may supply drug accountability forms that must be used or may approve use of standard institution forms. In either case, the forms must identify the investigational product, including batch or code numbers, and account for its disposition on a patient by patient basis, including specific dates and quantities. The forms must be signed by the individual who dispensed the drug and copies must be provided to Pfizer when directed.

At the end of the trial, the Sponsor or designee will provide guidance on the destruction of unused investigational product (eg, at the site).

5.7. Concomitant Treatment(s)

Concomitant treatment considered necessary for the patient's wellbeing may be given at discretion of the treating physician.

Medications intended solely for supportive care (ie, antiemetics, analgesics) are allowed.

All concomitant medications and treatments, including prescription, over-the-counter (OTC), herbal supplements, IV medications and fluids, supportive care (antiemetic treatment and prophylaxis), drugs used to treat adverse events or chronic diseases, non-drug supportive interventions (transfusions) will be recorded in the CRF from 28 days prior to the start of study treatment and up to 28 days post the last dose of study treatment.

Concomitant medications administered after 28 days after the last dose of trial treatment should be recorded for SAEs only as defined in [Section 8.14.1](#).

5.7.1. Prohibited Concomitant Medications

Medications or vaccinations specifically prohibited at study entry as specified in the exclusion criteria are also not allowed during the study treatment period, except for hematopoietic growth factors and steroids for symptomatic treatment (for details see [Section 5.8](#), Supportive Care).

If there is an important medical condition requiring any medication specifically prohibited during the trial, discontinuation from study treatment may be considered. The investigator should discuss the proposed course of action with the Sponsor Clinical Lead and/or Medical Monitor. The final decision on any supportive therapy or vaccination rests with the investigator and/or the patient's primary physician. However, the decision to continue the patient on study treatment requires the mutual agreement of the Investigator, the Sponsor, and the patient.

Patients are prohibited from receiving the following therapies during the Screening and Treatment Phase (including retreatment for post-complete response relapse) of this clinical protocol:

- Anti-cancer systemic chemotherapy or biological therapy.
- Immunotherapy not specified in this protocol.
- Investigational agents other than mogamulizumab or PF-05082566.
- Live vaccines (flu vaccination allowed).
- Glucocorticoids for any purpose other than to modulate symptoms from an event of clinical interest of suspected immunologic etiology, except as agreed upon by the Sponsor.

Consider withholding or discontinuing concomitant therapy with monoclonal antibodies of the same subclass as the study drugs (ie, IgG_K and IgG2) in patients where anti-study drug antibodies are detected while on-study.

The concurrent use of vitamins or herbal supplements should be considered with caution.

5.7.2. Concomitant Surgery

No formal studies have been conducted to determine whether there is a risk to perform concomitant surgery in patients under treatment with either PF-05082566 or mogamulizumab. As safety risks in this setting are unknown, it is suggested that the study drugs be withheld for 12 days before performing major surgery. This will provide a margin of safety of one drug half-life (for mogamulizumab, which has the longer half-life of the two study drugs) before resuming therapy with the combination.

Postoperatively, the decision to reinitiate PF-05082566 and mogamulizumab treatment should be based on a clinical assessment of satisfactory wound healing and recovery from surgery.

